Study Population	
Provider (OTs, SLPs, ATPs): 20
 
Caregivers of adult and pediatric patients: 20
 
Patients (adults and children): 20

Estimated # of Sites	Single Site: DESIN LLC will serve as the site and data will be gathered remotely and electronically using Qualtrics. Participants may reside anywhere in the United States. A description of the Qualtrics software and its capabilities, including data security features, is included later in this proposal.

Enrollment and Subject Participation Duration	
Staggered enrollment will occur over a 1- 3 month period. Participation in the study is approximately one week in duration including the trial of Obi Gen 3 and completion of the surveys. A follow-up semi-structured interview is optional and will not be conducted with all the participants. Follow-up interviews may be conducted with participants from any of the stakeholder groups whose responses require clarification or warrant further inquiry.

Primary Effectiveness Endpoint	
Assessment of user needs fulfillment after ~ one (1) week trial of Obi Gen3 using the following for each of the three (3) stakeholder groups as participants in the clinical investigation:
 
I.) Providers will complete - Survey specifically tailored to gather descriptive demographic data and inquire about their use experiences including whether their needs are fulfilled with the usability of Obi Gen3.
 
II.) Caregivers will complete - Survey specifically tailored to gather descriptive demographic data about the caregivers' use experiences and inquire about whether their needs are fulfilled with the Obi Gen3.
 
III.) Patients will complete: 1) Survey specifically tailored to gather descriptive demographic data about the patients' use experiences and inquire about whether their needs are fulfilled with Obi Gen3.

Primary Safety Endpoint	
Monitoring and recording of any adverse events through company's existing SOP120; None are anticipated due to the Class I device's low risk profile and the device's history of 0 adverse events.

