Modifications and new features undergoing development within Obi3 were evaluated with a safety risk assessment per SOP170, Safety Risk Management Procedures and ISO14971 a user interface formative evaluation (per IEC62366:2020) per IFD-DES-064 Formative Evaluation Plan, Obi3 (for results, see IFD-DES-070 Formative Evaluation Report, Obi3). These activities did not result in the identification of any new hazards, or potential use errors associated with the scope of Gen3 changes (see IFD-DES-018, Product Hazards Analysis Table). However, updates to the Product Hazards Analysis were made to correct for previous oversights or unintentional errors. Summative evaluation was not performed as the user interface as it pertains to safety is considered unchanged (see IFD-DES-072, Summative Evaluation Plan).

Fatigue or Frustration: Participants may experience mild fatigue, confusion, or frustration during initial use of the device, particularly during the learning phase. These effects are expected to be temporary and self-limiting. Participants will receive onboarding materials and optional technical support to reduce this risk.

Psychosocial Discomfort: Some participants may feel discouraged or self-conscious if they encounter difficulties using the device. The study includes an option to discontinue at any time and will collect feedback in a supportive, non-judgmental manner.

Data Privacy and Confidentiality: As the study collects identifiable information (e.g., stakeholder role, experience, and feedback), there is a theoretical risk of a breach of confidentiality or unauthorized data access. To mitigate this risk, all data will be collected via the

HIPAA-compliant Qualtrics platform, stored on secure servers, and accessed only by authorized study personnel.

d) Possible interactions with concomitant medical treatments as considered under the risk analysis.

ISO14971 related risk assessment has not identified any possible interactions with concomitant medical treatments (see IFD-DES-018, Product Hazards Analysis)

e) Steps that will be taken to control or mitigate risk.

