Subject Death - In the rare and unforeseen event of a participant's death during the study period, the site investigator or their designated representative must notify the IRB and DESIN LLC within 24 hours of becoming aware of the event. Death will be recorded as a reason for early study termination in the subject's CRF. While Obi Gen 3 is a Class I device with minimal risk, this reporting protocol ensures compliance with good clinical practice and transparency.

ii.) documentation of efforts to be made to trace subjects that are lost to follow-up and possible reasons

This study involves minimal risk and a short duration of participation for most subjects (approximately one week), with optional follow-up within one month for those whose survey responses warrant an optional semi-structured interview conducted by telephone. Despite this, the research team recognizes the importance of accounting for all enrolled subjects and will make reasonable efforts to trace those lost to follow-up. If a participant fails to complete the post-trial survey within one week following the designated trial period, the following steps will be taken:

- **Reminder Emails/Text Messages:** The HIPAA-compliant Qualtrics platform will send an initial automated reminder email and/or text message.
- **Follow-Up Contact:** If no response is received within 3–5 business days, study personnel will make up to two additional attempts to reach the participant by email, text, or phone. (if contact information is available).
- **Documentation:** All follow-up attempts will be documented, including date, time, method of contact, and any responses received.
- **Optional Withdrawal Confirmation:** If a participant expresses that they no longer wish to continue, this will be documented, and their status will be updated as voluntarily withdrawn.
- **Data Retention:** Any partial data collected before loss to follow-up will be retained and analyzed per IRB approval and applicable data use procedures.

Possible Reasons for Loss to Follow-Up May Include:

- Changes in caregiver or patient availability

- Loss of interest or perceived burden of participation
- Technology-related challenges (e.g., issues with email, survey links)
- Medical changes or competing life demands
- Unreachable contact information (e.g., email address no longer active)

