In-Office Assessment: Also part of SOP220, for screened subjects, their provider is sent a device for an in-office device assessment. During this time, the provider assesses whether the patient can use the device safely and effectively. This assessment is documented on DESIN LLC's D-FRM-021, Obi Medical Device Needs Assessment (MDNA). This form will also be filled out through Qualtrics.

Enrollment: The patients who pass pre-screening criteria per SOP220, and/or their legal authorized representative (LAR), would then be presented with the Informed Consent Form (ICF). At this time the Providers and Caregivers will also be invited to enroll in the study. Those patients who and/or their LAR sign both the ICF and study agreement, are considered enrolled in the study (Subject). Patients and/or their legal representative will be allowed ample time for review, consideration, and decision to participate in the study. A copy of the ICF should be provided to the subject and/or their LAR. After signing the ICF, the subject is assigned a sequential study number. These numbers are used for subject identification. The data platform, Qualtrics (HIPAA compliant) will be used to electronically enroll subjects.

Obi Trial: The screened subjects who pass the In-Office Assessment will take Obi home for a 7-day in home trial period in accordance with DESIN LLC's SOP220. Those subjects that complete the trial will then undergo a follow up office assessment with their provider. The providers will complete the secondary component of the MDNA form during the follow-up assessment.

Data Collection & Endpoints: Following the ~one week trial, subjects will be provided electronic links via Qualtrics to complete.

b) Description of those activities performed by sponsor representatives (excluding monitoring)

Sponsor representatives involved in this clinical investigation will engage in select study activities that support study implementation and participant engagement, while maintaining a clear separation from regulatory monitoring functions. [name], an employee of DESIN LLC (the study sponsor), will serve as a designated sponsor representative. In this role, she will perform the following non-monitoring responsibilities in direct support of the Principal Investigator, [name]:

- **Assisting with Participant Communication:** [name] will support recruitment and communication with potential and enrolled participants (providers, caregivers, and patients) throughout the study.

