The initial one-week trial period, while appropriate for assessing first impressions and short-term usability, may not fully capture longer-term use patterns, adaptation curves, or sustained satisfaction.

3. Subjective Nature of Usability Metrics

The surveys used in the study rely on self-report or stakeholder perceptions. These are inherently subjective and may be influenced by participant expectations, mood, or environmental factors during the trial period.

4. Potential for Response Bias

Given that participants know they are using a novel assistive device provided by a sponsor, there

is a risk of social desirability bias, especially among caregivers and providers who may want to provide favorable feedback. This risk will be mitigated through anonymized survey responses and neutral interview techniques.

5. Technological and Environmental Variability

Because the trial takes place in participants' home, school, or community settings, external variables (e.g., table height, feeding environment, caregiver supervision) may affect device use and outcomes. These contextual factors may be difficult to control or fully account for in analysis.

6. Small Sample Sizes in Subgroups

While the overall target sample size (N=60) is adequate for a usability study, subgroup sizes (e.g., pediatric patients or specific provider types) may be too small to detect nuanced differences or trends. This could limit the ability to draw robust comparisons across user types.

7. Missing or Incomplete Data

As with any study involving remote data collection, there is a risk of incomplete surveys, missed interviews, or dropouts. The study team has implemented follow-up reminders and contact protocols to maximize retention and response rates.

d) The Methods for addressing these factors in the clinical investigation

Despite these foreseeable factors, the mixed-methods approach, inclusion of validated usability tools, and efforts to mitigate bias strengthen the reliability of the study and support meaningful conclusions about the Obi Gen 3 device's real-world usability and design readiness. This usability study has been designed to address potential sources of bias, variability, risk, and data quality concerns through a combination of structured procedures, validated instruments, and robust data collection practices. The following methods have been implemented to ensure scientific rigor, participant protection, and the validity of study findings:

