- Internal testing procedures will be conducted prior to study launch to verify that skip logic, branching, scoring algorithms, and response piping function correctly across all instruments.
- A validation checklist will be completed to confirm alignment with the approved study protocol and data collection requirements. This includes verifying data field accuracy, response ranges, and user interface usability for all participant types.

Qualtrics is certified under HITRUST, ISO 27001, and FedRAMP, and is hosted on secure, encrypted servers that comply with the U.S. Health Insurance Portability and Accountability Act (HIPAA) and GDPR standards. Data are encrypted both in transit (TLS 1.2 or higher) and at rest, ensuring the protection of sensitive information submitted by participants. Access to the Qualtrics data dashboard is restricted to authorized research personnel only, with role-based permissions and two-factor authentication (2FA) enforced. Audit logs are automatically generated and maintained by the platform to track all system-level and user-level interactions with the data.

d) Procedures to maintain and protect subject privacy.

All subject data will be de-identified or coded using unique participant identifiers at the time of collection. No personally identifiable information (PII) will be linked to study data in the analysis datasets. Only authorized study personnel will have access to the master list that links identifiers to participant names, and this list will be stored in a secure, password-protected location accessible only to the Principal Investigator and designated research staff. All electronic data, including surveys and interview responses, will be collected using Qualtrics, a HIPAA-compliant, encrypted web-based platform. Data transmission will occur over secure (HTTPS) channels, and data will be stored on secure servers with access restricted by user roles and passwords.

For remote interviews, participants will be informed in advance about the nature of the questions and their right to withhold any information they are not comfortable sharing. No audio recordings will be

made without explicit permission, and any identifiable audio content will be transcribed, de-identified, and deleted upon completion of transcription and verification.

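### Survey answers are called anonymized as a safeguard against social-desirability bias, but the protocol's own procedures make them coded and traceable to named people

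*Protocol*

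**What the plan says.** Protocol A.6.4 c), item 4, notes that participants know the device comes from a sponsor and may answer favorably, caregivers and providers especially. It then states: "This risk will be mitigated through anonymized survey responses and neutral interview techniques".

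Other sections describe how the responses are handled:

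- A.6.4 a), Enrollment: "After signing the ICF, the subject is assigned a sequential study number". The number serves to identify the subject.
- A.8 d): "All subject data will be de-identified or coded using unique participant identifiers at the time of collection". It continues: "Only authorized study personnel will have access to the master list that links identifiers to participant names". The list is open to the Principal Investigator and designated research staff. Analysis datasets are to carry no personal identifiers.
- A.1.5 Synopsis, participation duration: interviews may be held with people from any stakeholder group "whose responses require clarification or warrant further inquiry". A.6.3 c) ii) and A.6.4 g) give much the same basis for contact.
- A.4 c), Data Privacy: "As the study collects identifiable information", with feedback among the examples given.
- A.6.3 c) ii): for people who do not return the survey, after an automated reminder "study personnel will make up to two additional attempts to reach the participant by email, text, or phone".

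A.7 i) has its own paragraph on response bias. It relies on telling participants that no answer is right or wrong and that candid feedback is welcome, and on electronic collection. It does not mention anonymity.

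**The concern.** Social desirability acts while the participant is answering. Anonymity helps only if an answer cannot be traced to the person who gave it. If the study team can trace a rating and telephone its author about it, the protection that item 4 relies on for the surveys is missing when it is needed.

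The user-needs results are self-reports about the sponsor's own product. The study has one group and no comparator (A.6.1 a)), is open-label, and plans no sensitivity analysis (A.7 n)). Nothing in the analysis would reveal inflated ratings. A final report that repeated item 4 would also credit the surveys with a property they did not have.

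**Working it through.** No arithmetic applies. The question is whether the procedures are compatible with anonymous answers, so each is set against what it requires the study team to know.

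| Provision | What must be known | Compatible with anonymous answers? |
|---|---|---|
| Study number at consent (A.6.4 a); explicit for patients) | which number is which person | only if surveys do not carry it |
| Codes and master list (A.8 d)) | which code is which name | no |
| Interviewees chosen from their answers (Synopsis; A.6.3 c) ii); A.6.4 g)) | which person gave which answer | no |
| Removal of a withdrawn person's data on request (A.6.3 c) i); A.7 m)) | which records belong to that person | no |
| Reminders and further contacts (A.6.3 c) ii)) | whether a person has answered | yes |
| Gift card on survey completion (Synopsis, Study Procedure) | whether a person has answered | yes |
| No identifiers in analysis datasets (A.8 d)) | nothing, but applies after collection | does not bear on the moment of answering |

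**Step 1: the two alternatives in A.8 d).** That section allows data to be either de-identified or coded. If surveys were stripped of any key at collection, nobody could be telephoned about a particular answer. The interview rule therefore requires the coded alternative, with the master list as the key.

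**Step 2: the groups affected.** The study-number sentence speaks of enrolled patients, whereas item 4 is most worried about caregivers and providers. The synopsis closes that gap, because it extends response-based interview selection to all three groups.

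**Step 3: which evidence carries the point.** The master list and the interview rule suffice. Reminders and payment show only that completion is tracked person by person, and they are not counted here.

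**Step 4: what is left of item 4.** It names two measures. Neutral technique acts on the interviews, and anonymization is the one that acts on the survey ratings. With that removed, the surveys still have the instruction in A.7 i) and electronic collection, neither of which depends on anonymity.

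**Step 5: the result exposed.** Under A.7 g), a user need passes when 50% of respondents among those who complete the trial are in favor. Favorable answers given out of courtesy count directly towards that proportion.

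**The case against.** The fair defence is that *anonymized* is loose wording for real privacy measures. Identifiers are kept out of the analysis datasets, results are reported in aggregate, dashboard access is role-based (A.8 c)), and the master list is restricted. The analysing Principal Investigator is kept out of direct recruitment and data collection (A.6.1 b)). The sponsor employee who deals with participants is excluded from data analysis (A.6.4 b)). All of this stands as confidentiality. It does not make an answer untraceable when it is given, which is what item 4 needs.

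Several stronger readings are tempting, but the documents do not support them:

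- *That response bias goes unaddressed.* Item 4 claims mitigation only, and the measures in its second half and in A.7 i) remain.
- *That the protocol treats this as the most likely bias.* It is one of seven factors in A.6.4 c), and they are not ranked.
- *That the sponsor employee who contacts participants reads their answers.* The documents do not say. A.6.5 lets the sponsor reasonably request subject report forms but does not mention this employee. The sponsor's ownership of the data (A.8 f)) does not show access to identified responses during the study.
- *That the effect on the 50% rule can be calculated.* One could assume a true rate of favor and a courtesy shift and compute the change in the chance of passing. That would measure an assumed total courtesy bias. The relevant quantity is the difference between coded and anonymous answering, and the documents give nothing on which to base it.

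**Conclusion.** The point holds as a contradiction about one named safeguard. The survey responses are coded and re-identifiable, so the mitigation specific to the surveys in A.6.4 c), item 4, is not delivered when participants respond. Other mitigations remain. The effect on the user-needs result cannot be sized from the documents; if it exists, the direction that item 4 itself fears is upward.

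The conclusion assumes that interviewees are in fact selected as the synopsis, A.6.3 c) ii) and A.6.4 g) describe. It assumes nothing about who at the sponsor sees individual responses. On that the document is silent, and the silence is worth ending.

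**What to change.** 1. In A.6.4 c), item 4, replace *anonymized* with *coded and confidential*, and stop citing anonymity as a mitigation.
2. List residual response bias as a limitation of the 50% user-needs result in A.7 g).
3. In A.8 d), state by role who can link survey answers to names.
4. Use the role permissions already described in A.8 c) to withhold individual-level survey responses from sponsor staff who contact participants until database lock. Except safety and device-deficiency reports, and align the sponsor's access to report forms in A.6.5 with this limit.
5. Tell participants about the limit at the start of the survey, since it can influence answers only if they know of it beforehand.

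The cost is wording, a permission setting and slightly slower sponsor access to individual feedback before lock. Reminders, payment, interviews by the investigators and removal of data on request can all continue.

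Making the ratings truly anonymous, with a separate opt-in for interviews, would be the alternative. It would give up removal on request and the link between a rating and the person's other study data, including the trial completion on which the A.7 g) rule is conditioned. Correcting the description and limiting access is the lighter change.
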